1.0 INTRODUCTION

This document is a clinical research protocol and the described study will be conducted in compliance with the IRB approved protocol, associated Federal regulations and all applicable IRB requirements.

This is a randomized study in patients with intermediate/high grade adult soft tissue sarcoma of the extremity or chest wall which will utilize an oral angiogenesis inhibitor versus placebo followed by neoadjuvant chemotherapy. The primary objective is to use FDG-PET to evaluate early response to antiangiogenic therapy with pazopanib. This will be correlated with pharmacokinetic analysis of pazopanib. Standard RECIST response to therapy will be measured and compared with FDG-PET results. The study will provide preliminary data on the relative contributions of pazopanib and chemotherapy with doxorubicin and ifosfamide as measured by changes in SUV by FDG-PET. Secondary objectives include: analyzing the safety of sequential pazopanib and neoadjuvant chemotherapy; measuring histologic response at the time of surgery as a surrogate marker of outcome; and evaluating tumor and serum biomarker response. The hypothesis is that the addition of pazopanib to preoperative chemotherapy with doxorubicin and ifosfamide will increase the overall response rate which could ultimately translate into an improvement in outcome for patients with resectable soft tissue sarcoma. The results of this study will inform the design and feasibility of a larger trial which would incorporate pazopanib as neoadjuvant therapy.

FDG-PET will be performed pre-treatment, after pazopanib, and after neoadjuvant chemotherapy to provide correlative, exploratory pharmacodynamic data on the anti-tumor effect of adding antiangiogenic inhibition to chemotherapy. Biomarker studies will also be performed including plasma measurement of VEGF and soluble VEGFR2 (sVEGFR2). Quantitative enzyme-linked immunosorbent assays (ELISA) for VEGF and sVEGFR2 will be performed on plasma and tumor extracts. Plasma will also be collected for micro RNA.

This is a pilot study to test the hypothesis that antiangiogenic therapy with pazopanib will enhance the response rate of front line chemotherapy agents as measured by radiologic response and tumor necrosis. This would provide the rationale to undertake a larger Phase II trial, randomizing patients to neoadjuvant chemotherapy with or without pazopanib, with progression-free and overall survival as end points.

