3.2 Secondary Objectives

- To examine the activity of antiangiogenic therapy with pazopanib combined with pre-operative chemotherapy for high risk extremity soft tissue sarcomas as measured by: Histological necrosis at surgery
Change in plasma and tumor biomarker assays of angiogenesis
- To evaluate the safety of sequential treatment with pazopanib and pre-operative chemotherapy with doxorubicin and ifosfamide.

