6.0 SUBJECT REGISTRATION AND RANDOMIZATION

All subjects will be registered by the coordinating center (University of Washington) and entered into the Protocol Accrual Tracking System (PATS). Information regarding the PATS system is available at http://www.cancerconsortium.org/rto/protocol_office/pats/. A complete, signed study consent and HIPAA consent are required for registration. An Investigator must review and sign the eligibility list for patients enrolled on the trial.

This is a double-blinded study. Patients will be randomized 2:1 to receive pazopanib versus placebo by the SCCA Investigator Drug Supply (IDS) Pharmacy according to a computer program from randomization.com. Physicians, research study staff, and patients will be blinded from the time of enrollment until the time of the patient's surgery, when unblinding will occur.

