G Pazopanib may be resumed 1 week after completion of post-operative therapy (chemotherapy +/- radiation) for those randomized to the treatment who had a response by imaging, to be continued for 1 year. Unblinding occurs during the first post-op visit after surgery.

H PEG-Filgrastim should be administered approximately 24-48 hours after completing chemotherapy. 10 days of filgrastim may be substituted.

I Mesna will be given at 400 mg/m². Post IFOS doses will be at 4 hours and 8 hours (+/- standard clinical dosing windows)

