7.6 Duration of Follow-Up

When a subject discontinues the study, a Final Visit will be conducted. All subjects will have one Follow-up Visit approximately 30 days after the Final Visit. This Follow-up Visit does not need to be performed for subjects who have had a Final Visit conducted \geq 30 days after discontinuation of maintenance pazopanib therapy.

Study visits and evaluations will be performed in clinic at Screening and within approximately 72 hours prior to hospital admission for each chemotherapy cycle (neoadjuvant as well as adjuvant). Assessments will include interval history, physical examination, blood counts and chemistries. Radiological assessments including FDG-PET CT, MRI of the primary tumor, and diagnostic CT chest will be performed prior to the 14 day Run-in period of pazopanib versus placebo. After the Run-in period, and prior to commencement of preoperative chemotherapy, subjects will undergo repeat FDG-PET CT and MRI of the primary tumor. After 2 cycles of chemotherapy, FDG-PET CT and MRI of the primary tumor will be repeated. (**Refer to Section 4.3 and Appendix A**). Study procedures may be performed up to approximately 72 hours before or after the scheduled visit date.

Subjects will be evaluated daily during radiation therapy. Following surgery, subjects who remain on pazopanib monotherapy will have study visits and evaluations monthly for the one year duration of therapy, and follow-up visits will be every 3 months for those not on pazopanib. CT of the chest without contrast will be performed every 3 months for the first

year following surgery and MRI (or CT) of the primary site of the tumor will be performed every 6 months.

Following the Final Visit and/or 30-day Follow-up Visit, follow-up will proceed as described in the study calendar (Appendix A) until recurrence or progression. Patients experiencing recurrence or progression will be contacted every 4 months for overall survival, unless the patient has withdrawn consent for the study has ended.

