8.2 Study-Specific Adverse Event Capture

8.2.1 Duration and Grade of Adverse Event Capture

All grade 3 and 4 adverse events occurring after the subject has taken the first dose of study drug until the end of study will be recorded in the subject's case record form.

Documentation must be supported by an entry in the subject's file. A laboratory test abnormality considered clinically relevant, e.g., causing the subject to withdraw from the study, requiring treatment or causing apparent clinical manifestations, or judged relevant by the Investigator, should be reported as an adverse event. Each grade 3 or 4 event should be described in detail along with start and stop dates, severity, relationship to investigational product, action taken and outcome.

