Descriptive displays of preliminary clinical endpoints (pathologic response, progression-free survival, overall survival) will compare response for the pazopanib and placebo groups, and will investigate the relationship between early pharmacodynamic response (by PET) and clinical endpoints. Response of high-risk soft tissue sarcoma to neoadjuvant chemoradiation therapy was estimated as 52% (38% no residual tumor, 14% ≥ 95 pathologic necrosis) in a series of 496 patients.[9] A smaller series found only 13/46 (28%) with $< 10\%$ viable tumor in surgical specimens following a variety of neoadjuvant regimens.[51] To direct planning of future studies, we will measure the rate of complete pathological response defined as greater than 95% necrosis in the surgical excision specimen. A 90% Wilson (score) binomial confidence interval will be computed for the rate of complete pathological response.

There are no stopping rules planned for toxicity, but safety will be monitored continuously. All subjects who are registered and receive at least one dose of study drug will be included in the safety analysis.

All reported adverse events will be coded using the Cancer Therapy Evaluation Program (CTEP) Common Toxicity Criteria version 4.0. The number and percent of subjects reporting adverse events (all, severe or worse, serious and related) will be quantified. Listings will be provided for all on-study deaths and adverse events that lead to withdrawal from study. Narratives of all serious adverse events and deaths on-study will be provided.

Correlative study assays will be analyzed using descriptive statistics, generally comparing pazopanib and placebo groups. Correlation will also be evaluated between pazopanib trough concentrations and drug exposure over the dosing interval (area-under-the-concentration-curve, AUC) in subjects consenting to the full intensive pharmacokinetic visits.

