APPENDIX A: Study Activities and Treatment Calendar

	Screening	End of Week Two	Prior to Day 1 of each cycle	After 2 cycles of preop chemo	At time of surgery	Post-treatment follow-up every 4 weeks if receiving pazopanib, else every 3 months
Informed Consent	X					
History/Progress Notes	X	X	X			X
Physical Exam	X	X	X			X
Vitals signs	X	X	X			X
Performance Status	X	X	X			X
Treatment Toxicity		X	X			X
Pathology Review	X				X	
CBC, chemistries, Ca ⁺⁺ , phos, Mg ⁺ , hepatic panel	X	X	X			X
UA	X		X			X
Pregnancy test	X					
INR	X					
ECG	X	X				X (every 3 months)
ECHO	X					
Tissue/blood for correlative studies	X	X		X	X	X (every 3 months)
FDG-PET	X	X		X		
MRI	X	X		X		
Plasma pazopanib trough level		X (2 visits)				X (every 3 months)
Full plasma pazopanib PK (optional)						X (once during Weeks 2-4)
CT-chest	X					X (every 3 months)

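### The adverse-event percentages in Section 14.1 have no time window or arm split, so up to 52 weeks of open-label maintenance is mixed into a safety objective about pazopanib followed by pre-operative chemotherapy

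*Combined protocol and SAP*

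**What the plan says.** All references are to the combined protocol and SAP.

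- **Objective.** Section 3.2: "To evaluate the safety of sequential treatment with pazopanib and pre-operative chemotherapy with doxorubicin and ifosfamide". Maintenance is not named. Section 1.0 gives the purpose: "The results of this study will inform the design and feasibility of a larger trial which would incorporate pazopanib as neoadjuvant therapy".
- **Summary.** Section 14.1: "The number and percent of subjects reporting adverse events (all, severe or worse, serious and related) will be quantified". The safety set is everyone registered who took at least one dose. Neither statement names a period or an arm.
- **Capture.** Section 8.2.1 records "All grade 3 and 4 adverse events occurring after the subject has taken the first dose of study drug until the end of study". Start and stop dates, relationship and outcome are recorded for each event.
- **Maintenance.** Section 7.0, note G, allows pazopanib to resume after post-operative therapy "for those randomized to the treatment who had a response by imaging, to be continued for 1 year". Section 11.4 makes this optional and requires a partial response by RECIST, PERCIST or both after the run-in.
- **Visits.** Section 7.6 sets visits for patients on maintenance "monthly for the one year duration of therapy, and follow-up visits will be every 3 months for those not on pazopanib". The Appendix A column that schedules toxicity review and laboratory tests is headed "Post-treatment follow-up every 4 weeks if receiving pazopanib, else every 3 months".
- **Blinding.** Section 6.0: "Physicians, research study staff, and patients will be blinded from the time of enrollment until the time of the" patient's operation. Note G places unblinding at the first post-operative visit. Either way, maintenance is open-label.

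**The concern.** Up to surgery, the arms differ by design only in the 14-day blinded run-in. After surgery, three further differences can arise, and all fall inside the capture window:

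1. Some pazopanib-arm patients take the drug for up to a year. No placebo patient can.
2. Those patients have about three times as many scheduled toxicity and laboratory visits as everyone else.
3. Relatedness is judged with treatment known.

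A percentage over the whole window therefore answers a different question from the one in Section 3.2. Split by arm, it would compare unequal exposure and unequal ascertainment. Pooled, it would still fold maintenance events into the result and would not show the arms at all. A later neoadjuvant trial needs the risk up to surgery. Two analysts choosing different windows could report different values for the same planned result, and a window chosen late would be chosen with treatment assignments known.

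**Working it through.** **The plan's own figure.** No figure is given for the adverse-event summary. The only design figure is about 90% power in Section 14.2 (21 patients, 2:1, difference 30, SD 20). With 14 and 7 patients and an assumed two-sided 5% level, 30 / [20·√(1/7 + 1/14)] = 3.24, and Φ(3.24 − 1.96) = 0.90. It reproduces, but it has no bearing on safety.

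**Exposure.** Run-in pazopanib is 14 × 2 = 28 patient-weeks. If k patients complete 52 weeks of maintenance, its share of pazopanib patient-weeks is 52k/(52k + 28):
- k = 1: 52/80 = 65%
- k = 3: 156/184 = 85%
- k = 7: 364/392 = 93%

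These are shares of drug exposure, not of adverse events.

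**Scheduled visits in a year.** On maintenance 52/4 = 13; otherwise 52/13 = 4.

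**Addition to the pazopanib arm's percentage.** A patient is newly counted only if not counted before maintenance (1 − q), if maintenance is started (f), and if an event occurs during it (m). The addition is (1 − q)·f·m. This assumes that q is the same in those who start maintenance as in the rest of the arm.

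None of the three is in the documents. For f, the Section 14.2 mean of −30% and a normal distribution give P(change < −30%) = Φ(0) = 0.5 for the percentage part of the PERCIST rule; I use 0.5 as an assumption. I take m = 0.3, also assumed.

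| q | Pazopanib arm | Pooled (× 14/21) |
|---|---|---|
| 0.3 | 0.7 × 0.5 × 0.3 = 10.5 points | 7 points |
| 0.6 | 0.4 × 0.5 × 0.3 = 6 points | 4 points |
| 0.9 | 0.1 × 0.5 × 0.3 = 1.5 points | 1 point |

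Over f = 0.25–0.75 and m = 0.2–0.6, the addition to the arm runs from:
- 3.5 to 31.5 points at q = 0.3
- 2 to 18 points at q = 0.6
- 0.5 to 4.5 points at q = 0.9 (0.1 × 0.25 × 0.2 to 0.1 × 0.75 × 0.6)

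The placebo arm gains nothing from maintenance.

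**Which q applies.** For any grade 3–4 event, q may well be high after doxorubicin and ifosfamide. For events typical of pazopanib and not already caused by chemotherapy, such as raised transaminases or hypertension, q is lower, so at the same f and m the addition is larger. Its ceiling as q approaches 0 is f·m, here 15 points.

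**Is time to surgery common to both arms?** Under Section 7.0, cycles 1–2 end at week 8 and surgery follows 2–4 weeks after pre-operative therapy, so the earliest date is about week 8 + 2 = 10. With cycles 3–4 and pre-operative radiation ending at week 21, it is about week 23 to 25. Cycles 3–4 depend on response (note C) and pre-operative radiation is optional (note D). Only the run-in has a nearly fixed window.

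**The case against.** The strongest reply is that Section 14.1 never promises a by-arm adverse-event table. Neighbouring sentences name the two groups for clinical endpoints and correlative assays; this one does not. A reader might infer that the plan commits to a biased between-arm comparison. The text does not support that: the imbalance between arms is conditional on a split being made. What stands is that neither the pooled nor the split version matches Section 3.2.

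A reader might also take 7 of 14 as a ceiling on maintenance uptake. It is not. A RECIST response alone qualifies under Section 11.4, while the 0.8-unit rule and patient choice pull the other way. Nor does the full f·m apply to the categories that Section 14.1 lists, because patients already counted during chemotherapy cannot be counted again. The visit imbalance matters mainly for silent, transient laboratory changes; a symptomatic grade 3–4 event does not wait for a scheduled visit.

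It can be said that capture might stop when protocol therapy ends, which Section 7.5 ties to completion of adjuvant treatment. But Section 8.2.1 does not use that term, the end of study is undefined, and Appendix A continues toxicity review during maintenance. Section 8.1 separates blinded and open-label portions, but only for reporting serious events.

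Finally, this is a secondary descriptive summary in a 21-patient pilot, with no test, stopping rule or decision threshold attached. Narratives of serious events and deaths, together with onset dates, would let maintenance events be identified afterwards. That is fair, and it limits the importance of the point.

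**Conclusion.** The point holds in a limited form. Followed as written, Section 14.1 mixes open-label maintenance events, available to one arm only and more closely observed, into the summary for an objective about pazopanib followed by pre-operative chemotherapy. The size cannot be computed from the documents. With f = 0.5 and m = 0.3 assumed, a by-arm percentage gains from about 1.5 to 10 points in the pazopanib arm as q falls from 0.9 to 0.3, and more for pazopanib-type events that chemotherapy has not already produced.

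A reader might infer that cutting at surgery makes the arms fully comparable. It does not, because the length and content of pre-operative treatment vary with response, which pazopanib is hypothesised to improve. No primary result is affected. The change is worth considering because it is cheap and fixes the window in advance.

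**What to change.** In Section 14.1, replace the adverse-event sentence with a plan to report the number and percent of subjects in each listed category as follows:

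- **By randomised arm, run-in:** onset from first dose to the start of cycle 1, washout included, as the fixed-window comparison.
- **By randomised arm, to surgery:** onset from first dose to surgery, or to the Final Visit if there is no surgery. Show the number of chemotherapy cycles and use of pre-operative radiation by arm alongside.
- **Post-operative chemotherapy or radiation:** a separate table.
- **Maintenance pazopanib:** a single uncontrolled group, with patient-weeks of exposure.
- **Relatedness** assigned after unblinding marked as open-label.

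All results stay descriptive. The cost is one paragraph, using onset dates already on the case report form; no visit, test or patient is added. The downside is smaller tables with wide intervals: with no events, the Wilson 95% upper limit, 3.84/(n + 3.84), is 21.5% for 14 patients and 35.4% for 7.

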14.2 Sample size justification

If the standard deviation for percent change in is 20% and the average change is 0% for placebo and a 30% decrease for pazopanib, there will be approximately 90% power to detect a difference between the placebo and pazopanib group in average percent change for n=21 and a 2:1 randomization.

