Relevant visit data should be entered on the CRF and any unused study medication will be accounted for and returned for all patients participating in the study, even for a brief period of time. Patients who discontinue following entry will have relevant information completed and recorded on the CRF. All patients who discontinue because of adverse events or clinically significant laboratory abnormalities should be followed up until they recover or stabilize, and the subsequent outcome will be recorded. If any patient should die during the trial or within 30 days of stopping study treatment, the Investigator will inform the IRB and the Novartis representative. The cause of death should be recorded in detail, within 24 hours, on a serious adverse event (SAE) form and reported to the IRB and Novartis.

Subjects who are withdrawn from the study prior to surgery will be replaced and randomized to treatment with pazopanib versus placebo according to the 2:1 design.

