14.0 STATISTICAL CONSIDERATIONS

14.1 Analysis plan

The primary objective is to compare FDG SUV (SUV lean, SUL) measures for patients receiving pazopanib and placebo. The primary endpoint is the percent change in SUV between baseline and the end of the 14-day Run-in period of pazopanib or placebo. The comparison will likely be conducted using a two-sided Wilcoxon rank sum test, often used as a nonparametric alternative to the two-sample t-test for studies with a small sample size. Additional endpoints will include SUV percentage change between baseline and the end of preoperative therapy, absolute post-treatment SUV (at 14 days and following preoperative chemotherapy), and absolute difference in SUV.

The analysis sample for the primary pharmacodynamic analysis is expected to exclude patients who have incomplete data due to missed PET scans or due to study withdrawal for toxicity. However, reasons for missing data will be examined, and multiple imputation will be considered if patients with incomplete data would be considered as part of the target population for future development of pazopanib in sarcoma. However, insofar as sarcoma is heterogeneous, the sample size is small, and covariates are limited – multiple imputation may not be applicable.

These pharmacodynamic response measures will be compared to tumor response by RECIST criteria, using graphical displays. Continuous measures of pharmacodynamic response (percentage change in SUL; response assessed using MRI) will also be compared to the trough plasma pazopanib, using graphical displays and correlation coefficients to investigate dose-response relationships related to patients' differing metabolism of pazopanib.

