14.3 Protocol Enrollment and Special Considerations

The ethnic and gender distribution chart below reflects estimates of race and gender of the population to be included in this study.

TARGETED / PLANNED ENROLLMENT: Number of Subjects			
Ethnic Category	Sex / Gender		
	Females	Males	Total
Hispanic or Latino	0	0	0
Not Hispanic or Latino	10	11	21
Ethnic Category Total of All Subjects*	10	11	21
a) Racial Categories			
American Indian / Alaska Native	0	0	0
Asian	0	0	0
Native Hawaiian or Other Pacific Islander	0	0	0
Black or African American	0	0	0
White	10	11	21
Racial Categories: Total of All Subjects*	10	11	21

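### Section 14.2 gives about 90% power without an alpha or a test; at an assumed two-sided 0.05, with normal data and a common SD, the Wilcoxon test that 14.1 calls likely has about 83%

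*Combined protocol and SAP*

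**What the plan says.** Section 14.2 is one sentence. It assumes that the SD of the percent change "is 20% and the average change is 0% for placebo and a 30% decrease for pazopanib", and concludes that "there will be approximately 90% power to detect a difference between the placebo and pazopanib group in average percent change for n=21" with 2:1 randomization. It gives no significance level, no sidedness and no test, and it does not say whether the SD applies to both arms.

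Section 14.1 defines the primary endpoint as the percent change in SUV from baseline to the end of the 14-day Run-in. On the test it says: "The comparison will likely be conducted using a two-sided Wilcoxon rank sum test", described as "often used as a nonparametric alternative to the two-sample t-test for studies with a small sample size". It gives no alpha either. The only confidence level in Section 14 is the 90% Wilson interval for pathological response, which is a different endpoint.

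On the number analysed, the table in 14.3 ("TARGETED / PLANNED ENROLLMENT: Number of Subjects") totals 21, the same number as in the power statement. Section 14.1 says the primary analysis sample "is expected to exclude patients who have incomplete data due to missed PET scans or due to study withdrawal for toxicity", then adds that "reasons for missing data will be examined, and multiple imputation will be considered" and that imputation may prove not to be applicable. Section 7.8 adds: "Subjects who are withdrawn from the study prior to surgery will be replaced and randomized to treatment with pazopanib versus placebo" in the 2:1 design.

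**The concern.** A power figure has meaning only for a stated test at a stated level. Here both are missing from the sentence that gives the power, and the section that mentions a test leaves it open and gives no level. Section 14.1 turns to a rank test because the sample is small. With 7 patients in the placebo arm, a large-sample formula, a t-test and an exact rank test give visibly different powers, so the reader needs to know which one the 90% refers to.

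This is the only planning figure for the primary comparison, and the Introduction says the results will inform a larger trial. A non-significant result will be read against the stated power. A 10% chance of missing the assumed effect supports a firmer reading than a 17% chance does. Leaving both test and level open also means that, with 21 patients, the choice between Wilcoxon and t-test, or between 0.05 and 0.10, could settle whether the result is called significant.

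**Working it through.** **Inputs from 14.2.** Difference in mean percent change 30 points (0% against a 30% decrease); SD 20; total 21 at 2:1, hence 14 pazopanib and 7 placebo.

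**Our assumptions.** Two-sided alpha 0.05, with 0.10 as the alternative; SD 20 in both arms; normal data unless stated; all 21 patients evaluable.

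**Standardised quantities.** d = 30/20 = 1.5. Noncentrality = 1.5 × √(14 × 7/21) = 1.5 × √4.667 = 3.240.

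**Step 1: reproduce the stated figure.** Large-sample normal formula, two-sided 0.05: Φ(3.240 − 1.960) = Φ(1.280) = 0.900. Solved for the placebo arm at 90% power: (1.960 + 1.282)² × 1.5/1.5² = 7.005, in effect 7 + 14 = 21. The stated figure reproduces.

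**Step 2: the two small-sample tests mentioned in 14.1.**
- t-test: noncentral t with 19 df and noncentrality 3.240.
- Wilcoxon: critical values from the exact null distribution of U for 7 against 14, power by simulation (400,000 trials per case, simulation standard error below 0.001).

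| Method | Two-sided 0.05 | Two-sided 0.10 |
|---|---|---|
| Normal formula | 90.0% | 94.5% |
| t-test | 86.7% | 93.0% |
| Exact Wilcoxon | 83.5% | 90.9% |

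The Wilcoxon rejection regions are U ≤ 22 or ≥ 76 (actual size 4.6%) at 0.05, and U ≤ 26 or ≥ 72 (actual size 9.4%) at 0.10.

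**Step 3: can the basis of n=21 be inferred?** Compare 21 with the next smaller 2:1 total, 18 (6 + 12).
- Normal formula at 0.05: needs 7.005 placebo patients, so 21.
- Normal formula at 0.10: (1.645 + 1.282)² × 1.5/1.5² = 5.71, so 18 would do.
- Exact Wilcoxon at 0.10: 84.7% with 6 + 12 and 90.9% with 7 + 14, so 21 is the smallest 2:1 total that reaches 90%.

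Two different bases therefore lead to 21, and the document does not say which was used.

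**Step 4: sensitivity of the Wilcoxon figure at 0.05.** The document gives no distribution, so these shapes are assumptions.
- Other shapes, 30-point difference and SD 20 in both arms: uniform 79%; log-normal post/baseline ratio (means 1.0 and 0.7, SD 0.20) 87%; Laplace 88%; t with 5 df 88%; left-skewed log-normal 88%; right-skewed log-normal 93%. With the normal case the range is about 79% to 93%, and one of the seven shapes reaches 90%.
- Normal data with unequal SDs (placebo, pazopanib): 25 and 17 gives about 77%; 15 and 22 about 89%; 10 and 24 about 90%.

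**Step 5: difference detectable with about 90% power at 0.05** (normal data, common SD 20). Wilcoxon: 87.8% at 32 points, 89.7% at 33, 90.6% at 33.5, so about 33 points. t-test: 90.6% at 32 points.

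**Step 6: evaluable patients.** With 13 + 7 evaluable, the Wilcoxon test at 0.05 has about 82%; with 12 + 6, about 75%. These counts only illustrate the dependence, because the document forecasts no number of exclusions.

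**The case against.** The strongest reply is that the 90% may be right as it stands. If the planners meant the Wilcoxon test at two-sided 0.10, a plausible level for a pilot, the power is 90.9% and 21 is the smallest 2:1 total that achieves it. This stands. A reader might infer from the exact match with the normal formula at 0.05 that n=21 was computed for a method other than the planned test, and so call the 90% an error. The document does not support that, because it is silent on alpha and both routes end at 21. The 90% Wilson interval in 14.1 does not settle the matter the other way, since it concerns pathological response.

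A second reply is that normal data with a common SD is an unfavourable benchmark for a rank test. This stands in part. Normal and uniform data give the two lowest powers of the seven shapes; the other five lie between 87% and 93%, within about 3 points of 90% or above it. Unequal SDs can raise or lower the figure. That is a reason to state the conditions with the figure; it does not show that 90% holds without them.

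A third reply is that replacement under 7.8 and possible imputation under 14.1 protect the number analysed. This is largely fair, and no power loss is charged to missing data here. Replacement does not, however, cover a patient who misses a PET scan without withdrawing.

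Finally, this is a pilot, the power is worded as approximate, and no decision rule in the document depends on 83% rather than 90%. This limits the weight of the point; the figure still needs a level and a test.

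**Conclusion.** The point holds in conditional form. At two-sided 0.05, with 14 and 7 patients evaluable, a 30-point difference, normal data and a common SD of 20, the test that 14.1 calls likely has about 83% power, and the t-test about 87%. The chance of missing the assumed effect is then about 17% (Wilcoxon) or 13% (t-test), against the 10% that 14.2 implies. Under those conditions the Wilcoxon test reaches the stated figure only if alpha is raised to 0.10, which is not declared for this endpoint.

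The conclusion rests on an assumed alpha, and the 83% rests on assumed shape and equal SDs: about 79% to 93% over the shapes tried, and about 77% to 90% over the unequal SDs tried. It would also be too strong to conclude that the trial is too small. At 0.10 the stated power is met, and at 0.05 about 90% power is available for 33 points instead of 30. The effect is modest and calls for no change in sample size or design.

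**What to change.** In 14.1, replace the tentative wording with one named test and a declared two-sided alpha for the primary comparison. In 14.2, restate the power for that test with its conditions. For example: *With 14 pazopanib and 7 placebo patients evaluable, two-sided alpha 0.05, normally distributed percent changes and a common SD of 20, the exact Wilcoxon rank sum test has about 83% power for a 30-point difference and about 90% for 33 points.*

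If the t-test is chosen at 0.05, state about 87% for 30 points. If two-sided 0.10 is intended with the Wilcoxon test, declare it and state about 91%. In each case say that the figure assumes all 21 patients are evaluable.

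The cost is two or three sentences, with no change to sample size, design or conduct. The downside is a less favourable stated power at 0.05, or an openly declared 10% type I error at 0.10.
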